### Research Questions and Hypotheses:

*Specific Aim 1: To determine the impact of service dogs and determine who benefits the most.*

**Hypothesis 1A:** Individuals partnered with SDs will have greater improved mental health over time (Primary outcome will be the PCL checklist. Secondary mental health will be quantified by scores on depression and alcohol use).

**Hypothesis 1B:** Individuals partnered with SDs will have improvements over time in secondary factors of physical, psychosocial, and socioeconomic variables. The secondary factors are defined as follows: 1) physical factors: co-morbidities, medication use, sleep 2) psychosocial factors: community participation, quality of life and 3) socioeconomic factors: demographic and health care utilization and out-of-pocket health care expenses.

*Specific Aim 2: To determine costs associated with total health care utilization and mental health care utilization among Veterans with mental health disorders needs and service or therapy dogs.*

**Hypotheses 2A:** Individuals partnered with SDs will have decreased mental health care utilization over time.

**Hypotheses 2B:** Individuals partnered with SDs will have decreased total health care utilization over time.

*Specific Aim 3: To determine recommendations for providing service dogs to Veterans.*

Develop a strategic plan to provide service dogs to Veterans. A consensus meeting will be planned and will include all investigators of the project along with key individuals from funding agency to discuss findings of study.

*Secondary Aim:* To compare study findings to another VA funded study that is providing dogs as pets to Veterans with PTSD. Both studies are using similar measures to assess mental and psychosocial factors. Data will be compared across groups (SD to dog as a pet) to determine if the highly trained dogs help the Veteran more than having a dog as a pet.

*Projected Time Table*

Training of SDs is time intensive and expensive, with limited numbers of dogs who actually graduate. We will work with vendors to obtain the dogs, but recognize that there may be a significant waiting period prior to pairing. To demonstrate maximum treatment benefits, the data collection phase of this three-year study will be conducted for a minimum 18 months (maximum of 24 months for early enrollees) as we feel the acclimation period for the human-animal bond is longer than 18 months. This allows sufficient time for statistical analyses.

*Timeline*

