#### *Measurements: Outcomes and Independent Predictors*

The outcomes to be measured by this study will be grouped into four categories: mental health, physical, psychosocial and socioeconomic/healthcare utilization. Table 2 shows an outline of the study outcomes, predictor variables, and possible confounders to be obtained from all participants.

Table 2: Measurements

	Constructs	Measures	Burden
Mental Outcomes	PCL -S	PTSD diagnosis/symptom severity	5 minutes
	Depression	PHQ-9	5 minutes
	Alcohol use	AUDIT-C	5 minutes Time point: baseline, final
Physical Factors	Co-morbidities	Medical record,	None to subject**

	Constructs	Measures	Burden
	Medication	Type, class, dose	None to subject **
	Sleep	Pittsburgh Sleep Index and PSQI Amendment for PTSD	10 minutes
Psychosocial Factors	Health-related Quality of Life	SF12	10 minutes
	Community participation	Community Integration Questionnaire	10 minutes
	Demographic	Age, gender, race/ethnicity, marital status	5 minutes
Service Dog	Satisfaction Tasks	Behavior, Level of satisfaction with the performance of service dog and what tasks are completed	10 minutes Follow up visits 1, 2, 3 and thereafter; only after pairing
Economics	Socioeconomic factors	Employment, hours worked, years of education, health insurance, income	5 minutes
	Healthcare utilization	Number of visits to healthcare in previous 3 month time period, for both mental health and general health care visits	
	Healthcare costs	Out of pocket expenses, self-report of outside healthcare	10 minutes

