**Analysis:** The distribution of each variable will be examined for outliers to determine if transformations (to normalize data) are necessary. Initially, means  $\pm$  SD, and medians, will be calculated for all continuous measures (e.g., age, psychological scales). Frequencies and percent will be determined for categorical variables (e.g., gender, race, etc.). Variables considered ‘confounders’ (demographic and dog predisposition questionnaires) would be compared across time for the relevant hypotheses. Categorical variables (e.g., gender, race, disability) will be compared across groups using chi-square. Continuous variables (years of disability, dog predisposition scores) will be compared using ANOVA. Baseline differences will be noted and controlled for in additional analyses. A significance level of ( $\alpha < 0.05$ ) will be used for all analyses. All data will be managed as intent to treat.

Statistical Analyses are presented below by hypothesis:

**Hypothesis 1A:** *Individuals partnered with SDs will have greater improved mental health over time.* Baseline data will be examined. Observed significant differences will be used as covariates in modeling, they will be controlled in subsequent analysis. For this hypothesis, a linear repeated measures mixed model will be used to determine changes over time between groups. PCL-checklist scores will be considered the dependent variable. Baseline PCL-C scores will be introduced in all models as covariates. These scores are continuous. The use of mixed models allows for control of covariance data expected in clustered and repeatedly sampled data, and missing data. We expect the SD group to have greater functional independence and community participation at the end of the study.

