**Hypothesis 1B:** *Improvements in secondary factors of physical, psychosocial, and socioeconomic variables will be seen in the SD group over time.* Variables within the physical (medication, comorbidities), psychosocial (affect, depression, loneliness) and socioeconomics (healthcare utilization) will be compared over time and will be assessed for each variable of interest using a repeated measures mixed model for dependent variable (DV) scored a continuous scale and generalized estimating equations (GEE) models for DV variables scored as a categorical. Dependent variables for all models will be scale or subscale scores. The within-participants variable will be the score at each time point (baseline, 3, 9, 12, 18 and 24 months). If significant differences exist at baseline for any confounding variables, that factor will be controlled for in the analysis. We expect to show improvements in all characteristics over the course of the study.

We will also complete a multivariate logistic regression to determine predictors of success (dichotomized higher scores after 18 months on function and participation). We expect that improvements in psychosocial factors (e.g, community participation) will result. We expect the data to be normally distributed; therefore, linear regression will be used. Results from the previous hypotheses (1B) will be used to determine which predictor variables are entered into the regression model; any variable with a  $p$ -value less than 0.10 will be considered. Highly related variables will be entered into the model separately. Any confounders significant at baseline will

Dogs and PTSD: V11: 11.26.14

be controlled for in the models. In addition, we will repeat the multivariate logistic regression analysis described above with group (SD vs. control) as a primary fixed variable. We expect that subjects paired with a SD will demonstrate increased improvement in psychosocial factors.

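### The Hypothesis 1B over-time models list affect and loneliness, for which no instrument is given, and do not list sleep, quality of life or community participation, which the hypothesis names and the trial collects

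*Combined protocol and SAP*

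**What the plan says.** Under Research Questions and Hypotheses, Hypothesis 1B defines its first two groups as "physical factors: co-morbidities, medication use, sleep 2) psychosocial factors: community participation, quality of life" and its third as "socioeconomic factors: demographic and health care utilization and out-of-pocket health care expenses". Depression and alcohol use are assigned there to Hypothesis 1A, as secondary mental health measures.

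In the section Measurements: Outcomes and Independent Predictors, the plan states that "Table 2 shows an outline of the study outcomes, predictor variables, and possible confounders to be obtained from all participants". The table has rows for sleep ("Pittsburgh Sleep Index and PSQI Amendment for PTSD"), quality of life (SF12), community participation ("Community Integration Questionnaire"), co-morbidities, medication, healthcare utilization and, in a separate row, out-of-pocket costs. It has no row for affect or loneliness.

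Under Data Management and Statistical Analysis, the Hypothesis 1B text reads: "Variables within the physical (medication, comorbidities), psychosocial (affect, depression, loneliness) and socioeconomics (healthcare utilization) will be compared over time". The entry at issue is "psychosocial (affect, depression, loneliness". Repeated measures mixed models or GEE are to be used. The Hypothesis 1A text names PCL scores as its only dependent variable and closes with an expectation: "We expect the SD group to have greater functional independence and community participation at the end of the study". The general analysis paragraph also treats dog predisposition scores as a confounder.

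**The concern.** A secondary analysis plan should test what its hypothesis predicts, using what the trial measures. Here the psychosocial entry of the analysis list shares nothing with the psychosocial entry of the hypothesis. An analyst following the text would find two models with no data and no named over-time test for three collected outcomes. Some departure from the text is unavoidable, and nothing in it says which.

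Two features add to the cost. The plan applies a 0.05 level to all analyses and states no multiplicity control, so a secondary outcome list settled after the data are seen would weaken those claims. The 1B results, screened at p below 0.10, also choose the predictors for the regression on who succeeds with a dog. A gap in the 1B list therefore carries into the question of who benefits most.

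**Working it through.** The plan gives no figure to reproduce here. The check is a comparison of three lists.

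| Construct | In Hypothesis 1B | In the 1B over-time list | Source or instrument given |
|---|---|---|---|
| Co-morbidities | yes | yes | medical record |
| Medication | yes | yes | medical record |
| Healthcare utilization | yes | yes | visit counts |
| Sleep | yes | no | PSQI, PSQI-A |
| Quality of life | yes | no | SF12 |
| Community participation | yes | no | CIQ |
| Out-of-pocket expense | yes | not by name | healthcare costs row |
| Demographic | yes | no | demographic row |
| Depression | no (1A) | yes | PHQ-9 |
| Affect | no | yes | none |
| Loneliness | no | yes | none |

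**Counts.** The hypothesis names 8 factors, the analysis list has 6 variables, and they share 3.
- On the list but not in the hypothesis: 6 − 3 = 3. Depression has an instrument, which leaves 2 (affect, loneliness) with none.
- In the hypothesis but not on the list: 8 − 3 = 5. Demographic characteristics are not an outcome that a dog could improve, and out-of-pocket expense is arguable (see below). That leaves 5 − 2 = 3: sleep, quality of life and community participation.

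**Are the missing three analysed elsewhere?** I read the rest of the analysis text for each.
- Sleep and quality of life are not named anywhere in it, from the general paragraph to the exploratory aim.
- Community participation is named. Participation is part of the success definition in the 1B regression, community participation is the section's example of a psychosocial factor, and it recurs in the exploratory analyses of the SD group. Community integration is also compared with the San Antonio dog-adoption study. None of these is the 1B test of improvement over time in the whole cohort.

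**Out-of-pocket expense.** The description of healthcare utilization among the measures says that it includes these expenses, so the listed utilization entry can cover them. Hypothesis 1B and Table 2 list the two separately. The text leaves this open.

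**Is there an affect or loneliness measure elsewhere?** Both appear as results of the earlier wheelchair service dog study under Preliminary Studies, and affect also in the second study there. The nearest text for this trial says that waiting Veterans will be asked about mood, without naming a scale. The 1B text also omits month 6, which the Design section schedules, as the earlier study's visits did. It is an inference, but the list looks carried over and not chosen.

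**The case against.** Much of the case on the other side is sound.

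- A reader might infer that four hypothesised outcomes go unanalysed. The documents do not support that. Out-of-pocket expense may sit within utilization, and community participation is analysed, though not in the over-time list.
- For sleep and quality of life the accurate word is *unnamed*. The 1B text applies its models to each variable of interest and says that dependent variables are scale or subscale scores. That fits the PSQI, SF12 and CIQ better than medication or co-morbidities. The exploratory sub-analysis promises repeated measures on all continuous variables. It compares groups split at baseline, however, and the plan concedes its limited power.
- A reader might also infer that the secondary outcomes are open to free choice. They are not: the hypothesis states them in advance and Table 2 fixes the instruments. This limits the selection risk.
- The expectation of functional independence under Hypothesis 1A is not an analysis, and the CIQ description links high scores to greater independence. I do not count it as an uncollected outcome.

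What survives is that the parenthetical list carries no wording to mark it as examples, although the same section uses such wording elsewhere. Read as written it is closed, and it disagrees with both the hypothesis and the measures.

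**Conclusion.** The point holds in this form. The 1B over-time list names two variables with no instrument and does not name three outcomes that are hypothesised and collected. Out-of-pocket expense is covered only under the broad definition of utilization. Depression is listed under 1B although the hypotheses place it under 1A.

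The conclusion assumes that the list is meant as complete and that Table 2 and the measure descriptions show everything collected. Table 2 is called an outline, but no other text supplies a scale for affect or loneliness.

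It would be wrong to read this as a threat to the primary result: the PCL model and the data collection do not depend on this list. It should be corrected before analysis, and it is not critical.

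**What to change.** 1. Replace the 1B list with the outcomes of Hypothesis 1B and Table 2, giving instrument and score for each: co-morbidities, medication, PSQI and PSQI-A, SF12, CIQ, healthcare utilization, and out-of-pocket expense as its own entry. Reconcile the utilization definition with that separate entry.
2. Delete affect and loneliness.
3. Move depression to Hypothesis 1A and add an explicit PHQ-9 repeated measures model there. Without that model the move would leave depression with no hypothesis-specific over-time analysis, since 1A models only the PCL.
4. Add a baseline-to-final AUDIT-C analysis under 1A, matching the two time points in Table 2.
5. Delete the reference to dog predisposition scores, for which no instrument is described.

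The cost is a wording change to the statistical section, best dated before the outcome data are examined. Every measure named here is already collected, so no new data and no change to the sample size are needed.

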### **Research Design and Methods**

#### *Design*

This 3-year, mixed methods modified, non-randomized trial will follow individuals for two years. Due to the inability to recruit veterans interested in participating in a control (no dog) group, this group has been eliminated going forward with the study. The study will examine the influence of SDs by assessing the longitudinal change in mental health assessment over time among veterans who have PTSD. The group will consist of individuals partnered with SDs. Following initial screening for inclusion criteria, including criteria set by dog vendors, subjects who are eligible will receive a SD. This study will measure changes over time in the primary outcome of mental health. Additional outcomes in psychosocial health and healthcare utilization will be included. Recruits successfully completing the screening process will be placed on a vendor's waiting list to receive a SD upon the dog's completion of training. Recruits who do not meet all criteria, including vendor criteria, will be ineligible to participate..

Data will be collected at baseline and at 3, 6, 9, 12, 18 and 24 months for individuals with service dogs. For those awaiting service dogs, repeated assessments will occur every 3 months until obtaining a SD. Once baseline data has been collected for 24 months, assessments will occur every 6 months until the Veteran is paired with a SD. Baseline data will include detailed information on the characteristics of the participants, their mental health, psychosocial well-being, socioeconomic and healthcare utilization characteristics. As we want to obtain information regarding the changes in health and wellbeing over time, a prospective study will permit this type of comparison.

*Sample:* The study will use a convenience sample of VHA patients who are currently in treatment for PTSD. We have chosen to use these criteria as a safety measure for the veteran and the dogs. At this time, there are currently 600 veterans receiving care at James A. Haley VAMC for PTSD, with an estimated 25 new veterans seen in the clinic per week. We are confident that an adequate number of Veterans will be recruited for the study. We will monitor recruitment and retention numbers on a monthly basis. The use of additional VA hospitals as a potential source for recruitment is the contingency plan should we be unable to meet enrollment numbers.

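### The predictors-of-success analysis under Hypothesis 1B names two incompatible models, leaves success undefined, and is repeated against a control group that the design has dropped

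*Combined protocol and SAP*

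**What the plan says.** Specific Aim 1 reads "To determine the impact of service dogs and determine who benefits the most". In the statistical analysis section, under Hypothesis 1B, the plan says "We will also complete a multivariate logistic regression to determine predictors of success" and describes success in brackets as "dichotomized higher scores after 18 months on function and participation". Two sentences later the same paragraph says "We expect the data to be normally distributed; therefore, linear regression will be used". Predictors are chosen from the data: the Hypothesis 1B results "will be used to determine which predictor variables are entered into the regression model", with p below 0.10 as the entry threshold. The paragraph ends by promising that "we will repeat the multivariate logistic regression analysis described above with group (SD vs. control) as a primary fixed variable".

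The Design section says "Due to the inability to recruit veterans interested in participating in a control (no dog) group, this group has been eliminated", and the only group it then describes is Veterans partnered with service dogs.

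Table 2 and the instrument descriptions list the Community Integration Questionnaire (CIQ, range 0 to 29) for participation and the SF12 for quality of life. No construct is labelled function.

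The paragraphs after Hypothesis 1B add an exploratory repeated-measures comparison of baseline-low and baseline-high Veterans, which hypothesises that lower scorers improve more. They also plan two multiple regressions of 18-month outcomes on baseline predictors, meant to describe who is likely to benefit relative to controls.

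**The concern.** A dichotomised outcome cannot be normally distributed, so the logistic and linear statements cannot both describe one analysis, and the closing sentence goes back to logistic. An analyst could defend either model after seeing the data.

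The outcome is equally open. Nothing says where the split falls, whether a Veteran must pass on one score or both, or whether a high score is judged against other Veterans or against the Veteran's own baseline. The most natural reading is a level at 18 months. On that reading, with no baseline adjustment, a Veteran who starts high and does not change counts as a success.

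The paragraph bears on who benefits most from a dog, which is half of Specific Aim 1. Aim 3 then turns the findings into recommendations for providing dogs. A level-based result could point those recommendations toward Veterans who were already doing well.

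**Working it through.** The plan gives no figure for this analysis, so there is none to reproduce. The contradictions are shown by comparing the text; the arithmetic illustrates what is at stake in the definition of success.

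**1. Model.** The Hypothesis 1B paragraph goes from logistic on a dichotomised score, to linear because the data are expected to be normal, and back to logistic for the repeat by group. No sentence assigns the two models to different outcomes.

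**2. Baseline adjustment.** The plan promises the baseline score as a covariate for the PCL models of Hypothesis 1A. For the predictors-of-success model, covariates come from the p < 0.10 screen and from confounders significant at baseline. The baseline value of the outcome score is therefore not guaranteed to enter.

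**3. Level versus improvement.** Let r be the correlation between the baseline and 18-month scores. Assumptions (not in the plan): bivariate normality, equal variances, median splits and no dog effect. Then:

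- P(high at 18 months | high at baseline) = 0.5 + arcsin(r)/π.
- Correlation of baseline with change = −√((1 − r)/2).
- Share of Veterans classified differently by level and by change = 0.5 − arcsin(√((1 − r)/2))/π.

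The plan states no r for these scores. Its sample-size paragraph assumes a first-order autocorrelation of 0.80, which is borrowed here only to set a range. Five visit steps from baseline to month 18 (months 0, 3, 6, 9, 12, 18) give 0.80^5 = 0.33. The Hypothesis 1B visit list omits month 6, which leaves four steps: 0.80^4 = 0.41. A constant correlation gives 0.80.

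| r | Success by level: baseline-high / baseline-low | Success by improvement: baseline-high / baseline-low | Classified differently |
|---|---|---|---|
| 0.33 | 61% / 39% | 30% / 70% | 30% |
| 0.41 | 63% / 37% | 32% / 68% | 32% |
| 0.50 | 67% / 33% | 33% / 67% | 33% |
| 0.80 | 80% / 20% | 40% / 60% | 40% |

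For example, at r = 0.80, arcsin(0.80)/π = 0.295, so the level figures are 0.795 and 0.205.

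Across the range, baseline correlates +0.33 to +0.80 with the 18-month level but −0.58 to −0.32 with improvement. The sign reverses, so a level definition works against the plan's own hypothesis that lower scorers improve more. The improvement column also arises with no dog effect (regression to the mean), so switching to raw change would only exchange one artefact for another. Adjusting for baseline avoids both for the other predictors.

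**4. Information lost by dichotomising.** Relative efficiency of a split at proportion p is φ(z)²/(p(1 − p)). At the median this is 0.3989²/0.25 = 0.637, a loss of about 36%. This applies only if the logistic sentence governs and the cut is at the median.

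**5. Comparator.** The design has one group. The external dog-adoption study has a wait-list arm, but the plan does not offer it as comparator here, and that study's assessments end at 6 months, not 18.

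**The case against.** The strongest reply is that this is one secondary item under Hypothesis 1B. It does not touch the primary PCL mixed model, and the plan addresses who benefits elsewhere, through the baseline-subgroup analysis of change and the two 18-month regressions. That stands, and it lowers the severity. It does not make the paragraph executable, and the overlap is itself a reason to reconcile the two places.

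Three stronger readings are tempting, and the documents do not support them:

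- **That success is certainly a level.** The phrase could mean higher than the Veteran's own baseline, and the paragraph speaks of improvements. Level is the more natural reading, and the companion regressions also take outcomes from the 18-month visit. The certain defect is that neither the baseline reference nor the cut-point is stated.
- **That function is not collected.** The SF12 and CIQ are collected, and one of their scores may be intended. What can be said is that no instrument is designated for it.
- **That the group term cannot be estimated.** Controls were dropped going forward, and the documents do not say whether any were enrolled earlier. What can be said is that no comparator is defined, with no number, role or analysis rule for any earlier controls. Leftover control wording is also spread through the document and is not peculiar to this paragraph.

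It is also fair to object that the percentages rest on an assumed median split and a correlation borrowed from a power calculation, and that they apply only without baseline adjustment. They are illustrations, not estimates for this trial.

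**Conclusion.** Wrong as written, and should be fixed. Three things are established from the text alone: the model is stated as both logistic and linear; success lacks a cut-point, a baseline reference, a rule for combining two scores and a designated function measure; and the analysis is repeated against a group that the design has eliminated, with no replacement comparator.

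The size of the problem depends on how success is read. As an unadjusted level, the illustration runs from 61% versus 39% (r = 0.33) to 80% versus 20% (r = 0.80) in favour of Veterans who started high, under the assumptions set out above. If a median split is used, about 36% of the information is lost. If the linear sentence governs, that loss does not arise. A reader might infer that Aim 1 as a whole fails; the documents do not support that, because this is a secondary analysis and other planned analyses bear on the same question.

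**What to change.** Replace the predictors-of-success model with one linear regression of the continuous 18-month CIQ score, and likewise of the PCL score, on prespecified baseline predictors, always including the baseline value of the same score. In the same revision:

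- drop the dichotomy;
- drop the function outcome, or name a collected score for it;
- replace the p < 0.10 screen with the prespecified list, so that the baseline score cannot be screened out;
- delete the service-dog-versus-control repeat under Hypothesis 1B and the matching claim of comparison with controls in the exploratory paragraphs;
- merge this analysis with the overlapping 18-month regressions, so that one model answers the question;
- describe the results as predictors of outcome after pairing, not of benefit versus no dog, which a single group cannot show.

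The cost is analysis-plan wording and the loss of a yes/no success label. No new data are needed.

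### The regression for predictors of success selects variables by whether their mean changed over time (Hypothesis 1B, p < 0.10), not by whether they relate to success

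*Combined protocol and SAP*

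**What the plan says.** Specific Aim 1 is "To determine the impact of service dogs and determine who benefits the most". One of the analyses serving it stands in Data Management and Statistical Analysis, under Hypothesis 1B: a regression for predictors of success, where success is a dichotomy of higher function and participation scores after 18 months. The entry rule is "Results from the previous hypotheses (1B) will be used to determine which predictor variables are entered into the regression model", and any variable with a p-value "less than 0.10 will be considered".

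The 1B results that feed this rule are described just above it. The variables are "Variables within the physical (medication, comorbidities), psychosocial (affect, depression, loneliness) and socioeconomics (healthcare utilization", and they "will be compared over time and will be assessed for each variable of interest using a repeated measures mixed model" (GEE if categorical). The plan adds "Dependent variables for all models will be scale or subscale scores" and "The within-participants variable will be the score at each time point (baseline, 3, 9, 12, 18 and 24 months".

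The paragraph does not say whether selected predictors enter as baseline or follow-up values. It also adjusts for confounders that are significant at baseline.

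Later in the same section, a separate exploratory analysis relates demographic and other variables to PCL and psychosocial outcomes. Its regressions take variables with p < 0.10 in univariate analysis, use the 18-month visit for the outcome, and use baseline for the predictors.

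**The concern.** A screen for a prediction model should use either a prior list or evidence that a variable is associated with the outcome. A 1B p-value is neither. It says whether the cohort mean of a variable moved between baseline and follow-up. A variable can move in everyone and be unrelated to who succeeds. Another can stay flat on average and separate successes from failures well.

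Four consequences follow from the rule as written:

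- Variables enter because they changed, whether or not they relate to success.
- Community participation is a 1B factor in the aims and also part of the success definition. Nothing stops it from entering as a predictor of itself.
- Sex cannot change and age advances equally for everyone, so a change test of either is not meaningful. PCL is the outcome of Hypothesis 1A, not 1B.
- Two selection rules for similar questions stand close together in the plan and are not reconciled.

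At stake is whether this model can contribute to the question of who benefits most, and through it to the provision recommendations of Aim 3.

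**Working it through.** The plan gives no figure for the performance of this rule, so there is none to reproduce. The main argument comes from setting the two rules side by side.

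| | Success regression (under 1B) | Later exploratory regressions |
|---|---|---|
| Outcome | Dichotomized success after 18 months | 18-month PCL and psychosocial outcomes |
| Selection p-value tests | Change over time in the candidate itself | Univariate relation of candidate to outcome |
| Threshold | 0.10 | 0.10 |
| Predictor timing | Not stated | Baseline |

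The outcome of the success regression appears nowhere in the test that selects its predictors.

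**Illustration of size.** Inputs from the documents:

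- n: 220 × (1 − 0.15) = 187, or the 200 completers the plan expects (Sample).
- Visits: baseline plus 5, so 6 (Hypothesis 1B).
- First-order autocorrelation 0.80 (the power paragraph under Sample).

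Assumptions not in the documents: normal data, equally spaced visits, linear change reaching d SD at the last visit, success in half the cohort, and an odds ratio (OR) for success of 1 to 2 per SD of the baseline value.

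The 1B screen was represented by a Hotelling T-squared test of any time effect at p < 0.10. The comparator was a t-test of baseline values by success status at p < 0.10. There were 2,000 simulated trials per row.

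| n | Change d | OR per SD | Passes 1B screen | Passes association screen |
|---|---|---|---|---|
| 187 | 0.2 | 1.0 | 52.4% | 11.2% |
| 200 | 0.2 | 1.0 | 55.9% | 9.5% |
| 187 | 0.3 | 1.0 | 85.8% | 9.1% |
| 200 | 0.3 | 1.0 | 87.6% | 10.7% |
| 187 | 0 | 1.5 | 9.1% | 85.3% |
| 200 | 0 | 1.5 | 10.2% | 87.1% |
| 187 | 0 | 2.0 | 10.2% | 99.7% |
| 200 | 0 | 2.0 | 12.3% | 99.9% |

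**Exact check of the 1B column.** Let m be the vector of mean visit-to-visit differences and C their covariance under autocorrelation 0.80. The test has a noncentral F distribution with 5 and n − 5 degrees of freedom and noncentrality λ = n·m′C⁻¹m, which for this linear change equals 0.7444·n·d².

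- d = 0.2: λ = 0.7444 × 187 × 0.04 = 5.57, pass rate 52%. With n = 200, λ = 5.96, pass rate 55%.
- d = 0.3: λ = 0.7444 × 187 × 0.09 = 12.53, pass rate 86%. With n = 200, λ = 13.40, pass rate 88%.
- d = 0: λ = 0, pass rate exactly 10%, whatever the OR. The simulated 9-12% is this value with simulation error.

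**Sensitivity to the form of the test.** For a single paired change, with d in SD units of the change score, the pass probability is about Φ(d√n − 1.645). At d = 0.20 and n = 187 this is Φ(2.735 − 1.645) = Φ(1.09) = 86%, against 52% for the six-visit test. The level depends on the test and the scale of d; the direction does not.

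**The case against.** The strongest reply is that the plan does study baseline traits. The later exploratory regressions use baseline predictors, include demographics, screen on association with 18-month outcomes, and aim to describe the Veterans most likely to benefit. A further sub-analysis asks whether lower baseline psychosocial scores go with greater improvement. This stands. A reader might infer from the 1B rule that the plan leaves out the characteristics a provider could use, and the documents do not support that. Those analyses do not repair the success regression, however: it has its own outcome and rule, and it does not refer to them.

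A second inference is that success is related to variables measured over the same follow-up. The text does not say so. Timing is simply unspecified.

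A third is that demographics can never enter. That is also too strong. The aims list "socioeconomic factors: demographic and health care utilization and out-of-pocket health care expenses" under 1B, so marital status or employment could change and pass, though only because they changed. Two side routes exist as well. One adjusts for confounders significant at baseline, but its meaning is unclear now that Design leaves one group. The other adds baseline PCL to all models, but stands under Hypothesis 1A, so its reach is arguable. Both are adjustment, not selection.

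Finally, the effect sizes above are assumed. That limits the percentages, not the mismatch between what the screen tests and what the model is for.

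**Conclusion.** The concern holds for the success regression under Hypothesis 1B and does not extend to the plan as a whole. The rule selects on mean change, which is a different quantity from association with success. Under the stated assumptions an irrelevant variable passes about 52-56% of the time with a 0.2 SD change and 86-88% with 0.3 SD, while a true predictor with a stable mean passes about 9-12%. Screening baseline values on association with success reverses this: about 85% to over 99% for true predictors and 9-11% for irrelevant changers.

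This is a secondary analysis and the primary PCL analysis is unaffected. It should still be corrected before the data are analysed, because the model as specified cannot reliably identify who benefits.

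**What to change.** In the success-regression paragraph under Hypothesis 1B:

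1. Delete the screen on 1B p-values.
2. Replace it with a pre-specified list of predictors measured before pairing, for example age, sex, baseline PCL, PHQ-9, PSQI, SF12, CIQ and employment. Since assessments repeat while Veterans wait for a dog, name which pre-pairing assessment supplies the values.
3. Exclude all post-pairing values, including follow-up values of the measures that define success. Baseline values of those measures may stay as predictors.
4. If a fixed list is not wanted, at minimum adopt the rule of the later exploratory regressions (baseline values, selected by association with the 18-month outcome), so that the two paragraphs agree.

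The cost is a few lines of text. The variables listed are already in Table 2, so no new data are needed. The downside is that fewer variables can be explored.
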